| Body Composition                  |                    |            |           |  |
| BMI (weight & height)                    | Calibrated digital | B, 12m     | 2 minutes |  |
|                                          | scales &           |            |           |  |
|                                          | stadiometer        |            |           |  |
| Waist and hip circumferences             | Tape               | B, 12m     | 3 minutes |  |
| Other                                    |                    |            |           |  |
| Physical activity                        | IPAQ  | B, 12m     | 5 minutes |  |
| Diet                                     | DINE  | B, 12m     | 5 minutes |  |
| HR quality of life                       | $EQ5D^{34}$        | B, 6m, 12m | 1 minute  |  |
| Health and other resource usage          | Case Report Form   | B, 6m, 12m | 4 minutes |  |

| Proportion maintaining weight |                       | 12m    |           |
|-------------------------------|-----------------------|--------|-----------|
| loss                          |                       |        |           |
| Binge eating                  | EDE-Q    | B, 12m | 1 minute  |
| Psychological well being      | GHQ12    | B, 12m | 3 minutes |
| Health-related behaviours     | AUDIT-C &             | B, 12m | 2 minutes |
| (alcohol consumption &        | HSI  |        |           |
| smoking status)               |                       |        |           |

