#### 10.2 Sample size

The sample size for the original study was 950 and based on detecting an effect size of 0.309 with 90% power at a significance level of 5%. Since this is now a feasibility study, the planned sample size will not be derived statistically. Instead the intended sample size is the number of participants it is possible to recruit based on our inclusion criteria over an 18 month period. Since recruitment has now closed our potential sample size is 170. This sample size allows us to estimate a percentage of 50% (the percentage with the greatest associated variability) to within 7.5 percentage points either side for the whole sample (n= 170), or to within 15.7 percentage points for percentages within each study arm (n = 39). These are the precisions that will be achievable for the estimation of the retention rate or any other proportion. As a feasibility study we are not primarily concerned with effectiveness, however we still feel it is informative to present the power we will have to detect differences. With our current sample size (n=170) and assuming 30% attrition, we have 39 in each of the three treatment arms. We will be able to detect a difference of 3.537 BMI points at the 5% significance level with 80% power between any two arms (our primary comparison was between the control group and the intensive arm). This is just over a difference of 9.75kgs between groups.

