#### 11.4 Economic evaluation

There are limitations to undertaking a cost utility analysis within a feasibility study. Although we will not be able to establish definitive cost utility results, we will apply a cost utility framework to estimate parameters and unknowns for future research. Direct costs will include all resources used in the delivery of the interventions (staff time, staff travel, materials, venue, etc.). These will be recorded prospectively in relevant units and valued using standard methods. All resources used in training professionals in motivational interviewing skills will similarly be prospectively recorded and valued. As training is a one off investment which produces a flow of benefits over time, training costs will be amortised similarly to equipment expenditures.

Indirect costs will include differential use of NHS resources. Health service resource use in primary care, secondary care and the community will be collected for participants in all 3 arms of the trial at baseline, 6 months (during the intervention) and at 12 months. Questions will relate to all health service contacts and prescription medicines dispensed in the previous 3 months. Patient recall has been shown to be a valid method for collecting health service resource use data over this period. Health service resource use will be valued using standard sources. All costs relating to weight loss/maintenance activities such as use of gyms will be recorded. It is important to monitor these costs as the intervention may be substituting for some activities, for example weight loss group sessions by participants in the control group. Mean differential costs will be estimated. As cost data are often skewed, tests for normality will be applied. If distributions are shown to be nonnormal, non-parametric bootstrapping methods will be used to test for mean cost differences between groups.

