The main effectiveness measure in the economic evaluation will be the EQ-5D (EuroQol) quality of life instrument which will be administered alongside the resource use questionnaire. EQ-5D scores allow estimation of quality adjusted life years (QALY). Cost effectiveness will be based on between group differences in costs and EQ-5D scores. This is the method of economic evaluation preferred by NICE as the resulting cost utility estimates can be compared not only with other weight control programmes, but also with unrelated health care interventions. Results will be reported in the form of incremental cost utility ratios (incremental cost/QALY). A cost effectiveness acceptability curve will show the probability of the more costly intervention having an incremental cost utility ratio below a range of acceptability thresholds. A series of one way and multivariate sensitivity analyses will be undertaken to assess how sensitive results are to changes in the assumptions used and these analyses will be key given that this is a feasibility study.

At present, there is a paucity of evidence on how changes in BMI are related to changes in EQ-5D. We will therefore undertake a secondary analysis with BMI as the effectiveness

measure. Difference in the two analyses will contribute to the evidence on the relationship between these two measures.

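### Read literally, the acceptability curve's ratio-below-threshold definition counts dearer-and-worse results as cost-effective; a one-line net-benefit wording removes the problem

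*Protocol*

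**What the plan says.** Protocol section 11.4 bases the comparison on differences between groups: "Cost effectiveness will be based on between group differences in costs and EQ-5D scores". The summary is a ratio: "Results will be reported in the form of incremental cost utility ratios (incremental cost/QALY"). Uncertainty is shown by a cost-effectiveness acceptability curve, described as "the probability of the more costly intervention having an incremental cost utility ratio below a range of acceptability thresholds", with a citation to a general health-economics methods text (reference 63).

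The section has no net-benefit rule, no rule for negative ratios and no mention of quadrants of the cost-effectiveness plane. It mentions bootstrapping only for testing mean cost differences when cost data are non-normal, and does not say how the probabilities on the curve will be generated.

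The section also limits its own claims: "Although we will not be able to establish definitive cost utility results, we will apply a cost utility framework to estimate parameters" and unknowns for later research. EQ-5D is collected at baseline, 6 and 12 months (section 8.1, Table 1). Section 10.2 gives the numbers expected at analysis: "With our current sample size (n=170) and assuming 30% attrition, we have 39 in each of the three treatment arms".

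**The concern.** A cost-per-QALY ratio can be compared with a threshold only when the QALY difference is known to be positive. An intervention costing £500 more and losing 0.02 QALY has a ratio of 500 / (−0.02) = −£25,000. That number is below every non-negative threshold, yet the intervention is dominated. If an intervention is cheaper and less effective, the ratio is positive again and the direction reverses: a ratio below the threshold is then the unfavourable result.

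Restricting the sentence to the more costly intervention does not help. With the cost difference positive, every negative ratio is a dominated one. The wording would be harmless if the QALY difference were almost certainly positive. With about 39 participants per arm, that depends on a true effect and a QALY SD that the protocol does not state.

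At stake is the one display of cost-utility uncertainty that the protocol names. Followed literally, it could show a high probability of cost-effectiveness for an intervention with no QALY benefit, and a higher one still for an intervention that reduced QALYs.

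**Working it through.** **Inputs from the protocol.** The number per arm is in section 10.2: 170 × 0.7 / 3 = 39.7, stated as 39. The curve's definition is in section 11.4. The protocol gives no QALY difference, QALY SD, cost difference, cost SD or threshold value, so it has no figure for the curve to reproduce.

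**Assumed inputs (not in the protocol).** QALY SD 0.15, 0.20 and 0.25; mean extra cost £500; cost SD £1,500; threshold L = £20,000 per QALY; normal, independent errors.

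**Algebra.** Write dE for the QALY difference, dC for the cost difference and NB = L × dE − dC.

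- Literal curve: P(dC/dE < L). Multiplying through by dE keeps the inequality when dE > 0 and reverses it when dE < 0, so this equals P(dE > 0 and NB > 0) + P(dE < 0 and NB < 0).
- Correct curve: P(NB > 0).
- If dC > 0 and dE < 0, then NB < 0 for every L ≥ 0. So, given dC > 0, literal minus correct = P(dE < 0 | dC > 0), the same at every threshold.

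This step needs no assumed value.

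**Standard errors.** √(2/39) = 0.2265. SE(dE) = 0.15, 0.20 or 0.25 × 0.2265 = 0.034, 0.045 or 0.057. SE(dC) = 1,500 × 0.2265 = £340.

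**Correct curve with no QALY gain.** P(NB > 0) = Φ(−500 / √[(20,000 × SE(dE))² + 340²]).

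- SD 0.15: Φ(−500/760) = Φ(−0.658) = 0.26
- SD 0.20: Φ(−500/967) = Φ(−0.517) = 0.30
- SD 0.25: Φ(−500/1,182) = Φ(−0.423) = 0.34

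**Literal against correct curve at £20,000 per QALY** (simulation, 4,000,000 draws):

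| True QALY gain | SD 0.15 | SD 0.20 | SD 0.25 | Gap |
|---|---|---|---|---|
| −0.02 | 0.83 v 0.12 | 0.84 v 0.18 | 0.85 v 0.22 | 0.63 to 0.71 |
| 0 | 0.74 v 0.26 | 0.79 v 0.30 | 0.83 v 0.34 | 0.49 |
| +0.02 | 0.72 v 0.45 | 0.78 v 0.46 | 0.82 v 0.47 | 0.27 to 0.35 |
| +0.05 | 0.81 v 0.74 | 0.83 v 0.70 | 0.85 v 0.66 | 0.07 to 0.18 |
| +0.10 | 0.98 v 0.98 | 0.95 v 0.94 | 0.94 v 0.90 | below 0.04 |

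Keeping only draws with dC > 0, the gap equals P(dE < 0) = Φ(−gain/SE(dE)): 0.50 at no gain and 0.07 to 0.19 at +0.05. At a threshold of £0 with no gain, the literal curve reads 0.50 and the correct one 0.07.

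Correlations of −0.3 to 0.3 between dC and dE leave the gaps within about 0.01 of those shown.

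The literal curve also misorders interventions: at SD 0.20 it gives 0.84 for a true loss of 0.02 and 0.78 for a true gain of 0.02.

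**The case against.** The strongest reply is that the sentence describes a curve and does not prescribe a counting algorithm. Saying that an acceptability curve shows the probability of the ratio lying below a threshold is common shorthand, and a methods text is cited. Nothing says that negative ratios will be counted as favourable, and the curve's computation may be set out in an analysis plan that is not shown. This stands as far as intent goes: the document does not show that the health economist would count dominated results as successes. It does not rescue the wording, which is the only definition given and produces the wrong answer if followed.

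Second, every QALY and cost input above is assumed. This stands too. The size is conditional and becomes small if the intervention is clearly better; only the algebra is unconditional.

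Two stronger readings are tempting. A reader might infer that wording the curve for a single more costly intervention is an error in a three-arm trial. The protocol does not support that: the primary contrast is intensive against control (section 1.3), section 11.1 compares each intervention group with control, and pairwise curves fit that design. A reader might also infer that the curve would mislead the decision on a larger trial. The protocol ties no progression decision to it, calls the cost-utility analysis preliminary (section 9), and reports incremental ratios and mean cost differences alongside.

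**Conclusion.** The point holds as a minor correction to wording. As written, the definition treats dearer-and-worse results as cost-effective at every threshold, and nothing else in section 11.4 prevents this. Given a positive cost difference, the overstatement equals the probability that the QALY difference is negative.

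Under the assumptions listed, that is about half a unit of probability at no QALY gain, falling to 0.07 to 0.19 at a gain of 0.05 and to less than 0.04 at 0.10. The protocol does not establish that its own curve would be inflated by any particular amount. The feasibility conclusions and the BMI analysis are unaffected.

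**What to change.** Replace the description of the curve in section 11.4 with wording such as: for each threshold L, and for each intervention-versus-control contrast, the cost-effectiveness acceptability curve will show the probability that L × (QALY difference) − (cost difference) is greater than zero. Add that any incremental ratio will be reported with the quadrant of the cost-effectiveness plane in which it falls, so that a negative ratio cannot be misread.

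If an analysis plan already defines the curve through net benefit, it is enough to align this sentence with it. The change needs no extra data or participants, only one or two sentences of text. Where the sign of the QALY difference is uncertain, the curve will look less favourable than a literal count would.

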#### 2.2 Rationale for current study/trial

The proposed study will evaluate an intervention based on 2 main components: **Motivational Interviewing** (incorporating implementation intentions) and **self regulation** (self monitoring). The overarching theme of the intervention is motivation. Motivation is central to many theories seeking to explain behaviour change. Motivation is unlikely to be static and will be a product of internal and external factors related to the individual. Since prolonged intervention contacts have been shown to help sustain weight loss, and attrition from longer term programmes is a problem, motivation is likely to be a key factor. Many people are able to become motivated enough in order to lose weight by dieting and/or exercise. However, maintaining these behaviours seems to be challenging and therefore enhancing motivation will be crucial to continued maintenance of healthy behaviours.

Motivational Interviewing will therefore be the key ingredient of the intervention. Motivational Interviewing (MI) is a client-centred technique, emphasizing personal autonomy, which enhances motivation for change. It is based on the well established

concepts of causal attributions, self efficacy and cognitive dissonance. MI has been shown to be effective as an adjunct to a behavioural weight control program.  It can be useful in maintaining behaviour change as well as initiating change  and it will support participants in an ongoing, tailored way.

RCTs and systematic reviews of MI approaches have shown that it can be used successfully in interventions to change both diet and exercise even when delivered by telephone. Brief interventions using MI have been effective in different areas of behaviour change including diet and exercise. There is some evidence that MI can be effective when only one session is given and even when sessions are as short as 15 minutes. One meta analysis examining MI in different areas of disease showed a combined effect of MI on decreasing BMI of 0.72 (p<0.0001) and found that longer follow-up increased the chance of an effect from 36% at 3 months to 81% at 12 months or longer.

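### The economic section asks how changes in BMI relate to changes in EQ-5D, but the only method it states compares two between-arm analyses, which suits that question poorly; a participant-level regression on the planned data would address it better

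*Protocol*

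**What the plan says.** Section 11.4 of the protocol makes EQ-5D, converted to QALYs, the main effect measure of the economic evaluation and sets the level of analysis: "Cost effectiveness will be based on between group differences in costs and EQ-5D scores". Results are to be incremental costs per QALY.

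The section then gives the reason for a second analysis: "there is a paucity of evidence on how changes in BMI are related to changes in EQ-5D". The second analysis uses BMI as the effect measure, and its purpose is stated as: "Difference in the two analyses will contribute to the evidence on the relationship between these two measures".

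Table 1 (section 8.1) schedules BMI at baseline and 12 months and EQ-5D at baseline, 6 and 12 months, on the same participants. Sections 11.1, 11.2 and 11.4 describe no analysis that relates the two measures within participants.

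On size, section 10.2 says: "With our current sample size (n=170) and assuming 30% attrition, we have 39 in each of the three treatment arms", and "We will be able to detect a difference of 3.537 BMI points at the 5% significance level with 80% power between any two arms". Section 11.1 regards a significant difference as unlikely unless the effect is far larger than that of other interventions. Section 2.2 cites a combined effect of motivational interviewing (MI) on BMI of 0.72.

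**The concern.** The question concerns people: when someone's BMI changes, does their EQ-5D change too, and by how much? The stated method concerns arms. Two cost-effectiveness results from the same trial differ only in their effect measure, so comparing them adds nothing beyond the arm differences in QALYs and in BMI.

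This has two consequences. If the arms differ little in BMI, a real within-person relationship will hardly show. If MI contact improves well-being by a route other than weight, the arm differences can suggest a BMI-to-EQ-5D link that is not there. The second is plausible on the protocol's own terms: psychological well-being is a secondary outcome, and section 8.2 says the intervention may change psychological distress.

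At stake is one parameter for later modelling. Section 11.4 says that estimating such parameters is the purpose of the economic work.

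**Working it through.** **1. The protocol's own figures.** 170 × 0.7 = 119, and 119/3 = 39.7, taken as 39 per arm, so 117 in all. The precision half-widths reproduce: 1.96 × √(0.25/170) = 7.5 points and 1.96 × √(0.25/39) = 15.7 points. No SD is given for the 3.537-point detectable difference. It implies 3.537 / [(1.96 + 0.842) × √(2/39)] = 5.58 by normal approximation, or 5.50 by a t-test. The figure therefore reproduces only on that back-calculated SD. No figure is given for the BMI/EQ-5D relationship.

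**2. What the comparison contains.** Let ΔC, ΔQ and ΔB be the arm differences in cost, QALYs and BMI. The two results are ΔC/ΔQ and ΔC/ΔB. Dividing the second by the first gives ΔQ/ΔB, because the cost cancels. A qualitative comparison (does one measure favour the intervention and the other not?) uses the same ΔQ and ΔB. With three arms there are only two independent contrasts.

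**3. Assumptions (not in the protocol).** SD of change 2.4 for BMI and 0.25 for EQ-5D; within-person correlation r = -0.3; change in EQ-5D to 12 months standing in for the QALY difference. The true slope is then -0.3 × 0.25/2.4 = -0.031 per BMI point.

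**4. Precision of the arm-level route.** SE(ΔB) = 2.4 × √(2/39) = 0.54. SE of the EQ-5D difference = 0.25 × √(2/39) = 0.057. A 1-point BMI effect acting only through the slope moves EQ-5D by 0.031, about half of one standard error. Simulating the intensive-control ratio gives:

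| True BMI effect | 95% range of ratio | Right sign |
|---|---|---|
| none | about -1.2 to +1.1 | 60% |
| 0.72 | about -0.5 to +0.5 | 67% |
| 1.0 | about -0.3 to +0.2 | 71–72% |

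The ratio is heavy-tailed, so the limits move with the random seed; the first row reached -1.4 to +1.2 in another run.

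Other assumed SDs (BMI 2.5, EQ-5D 0.2; slope magnitude 0.024, with BMI reduction counted as positive) give -0.38 to 0.45 with 33% wrong sign at 0.72 points, and -0.04 to 0.09 with 18% wrong sign at 1.7 points (0.309 × 5.50). At 3.537 points the wrong sign falls to 3%. The arm-level route becomes usable only near the detectable difference, which section 11.1 does not expect to see.

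**5. Precision of the participant-level route.** Power = Φ[atanh(|r|) × √(N - 3) - 1.96], with N = 117 and √114 = 10.68.
- |r| = 0.3: 0.3095 × 10.68 - 1.96 = 1.345, power 91%.
- |r| = 0.2: 0.2027 × 10.68 - 1.96 = 0.205, power 58%.
- |r| = 0.1: power 19%.
- 80% power needs |r| = tanh(2.80/10.68) = 0.26.

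This power depends on r and N, not on the assumed SDs. At r = -0.3 the simulated slope has a 95% range of -0.050 to -0.013, whether or not the arms differ.

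**6. Direct effect of MI on well-being.** Set r = 0, a 1-point BMI effect and a direct EQ-5D gain of 0.05. The arm-level ratio centres near -0.05 although no within-person link exists, with a wide 95% range of about -0.45 to +0.19. The regression adjusted for arm rejects in 5% of trials, its nominal rate.

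**The case against.** The protocol's claim is modest. It speaks only of contributing to the evidence, and section 11.4 already disclaims definitive cost-utility results. That stands, and it limits the importance of the point.

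A reader might infer that the protocol means to subtract pounds per BMI point from pounds per QALY, which would be meaningless. The text does not say so. The word can be read qualitatively, as asking whether the two analyses reach different conclusions, and that is a sensible reason to run both. The point therefore cannot rest on the subtraction, and it does not: the qualitative reading uses the same two arm differences, with the same imprecision.

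The arm-level ratio is not invalid in principle. It is a Wald-type estimate that would serve if the BMI difference were sizeable and MI affected EQ-5D only through BMI. The regression has its own weakness: illness, life events, mood or medication can move both measures, and the simulations above do not include such confounding. The two routes estimate different quantities, so greater precision does not make one right and the other wrong. The regression does match the question as the protocol words it.

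Model details could be left to a statistical analysis plan, which is not at hand and might add a participant-level analysis. That does not remove the point, because the protocol states a method for this aim, and that method suits the aim poorly.

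**Conclusion.** The point holds as a minor one. The only method stated for relating BMI change to EQ-5D change compares arm differences that the protocol thinks unlikely to reach significance, and a direct effect of MI on well-being could contribute to them. Under the assumed SDs and r = -0.3, the 95% range of the arm-level ratio spans zero and is many times wider than the true slope, for BMI effects from none to 1 point.

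Two stronger readings go too far. One is that the planned data would certainly reveal the relationship: that depends on |r| being about 0.26 or more for 80% power. The other is that the arm-level comparison would usually suggest a false link: in the direct-effect scenario its range is too wide for that.

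The SDs, the correlations and the use of 12-month EQ-5D change in place of QALYs are assumptions. The algebra in step 2 does not depend on them. The feasibility outcomes, the BMI comparison and the sample size are unaffected.

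**What to change.** Replace the last sentence of section 11.4 with: 'The relationship between the two measures will be explored by regressing each participant's change in EQ-5D from baseline to 12 months on their change in BMI, adjusted for trial arm and for baseline values of both. The slope per BMI point will be reported with its 95% confidence interval. This analysis is exploratory and observational, and is open to confounding, for example by illness or life events.'

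Keep cost per BMI point as a separate secondary result, without using it as evidence on how the two measures are related.

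The cost is one extra exploratory analysis on data already scheduled, with no added visits, questionnaires or participants. Its estimate is not causal and may be inconclusive if the true correlation is weak.
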